Total joint arthroplasty (TKA) is viewed as one of the most successful orthopedic surgeries for most end-stage joint diseases. In recent years, the concept of enhanced recovery after surgery (ERAS) has greatly improved the speed of rehabilitation after total joint arthroplasty. Patients feel more comfortable during the perioperative period and have shorter hospital stays with the administration of steroid administration. Dexamethasone plays an important role in ERAS due to its anti-inflammatory and pain reduction role. As, TXA can prevent the activation of plasminogen and delay fibrinolysis and reduce blood loss and the rate of blood transfusion perioperatively. Recent studies showed that dexamethasone may be administered multiple times peri operatively. A large number of studies confirmed that dexamethasone can reduce post operative pain and inflammation and shortens the length of hospital stay and combination pre operative tranexamic acid with dexamethasone reduces the limb swelling that improves the joint range of motion. There will be no risk of the interventional drug

Benefits will include that the drug is cost effective, easily available, reduce the post operative complications

3. Rationale

Previous studies showed the effects of peri-operative use of single dose of dexamethasone, and there is very little data available on effects of peri-op use of multiple doses of dexamethasone. There is no study that has been conducted yet, which compared the effects of peri-op use of 1 dose of dexamethasone and tranexamic acid with 2 doses of dexamethasone and tranexamic acid, on post operative range of motion and pain during rest and weight bearing on operated limb, length of stay in hospital and C-reactive protein.

4. Study Objectives

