4.1 Primary Objective

To evaluate the effectiveness of peri operative intravenous 2 doses of dexamethasone in lower limb joint/s replacement surgeries on postoperative C-reactive protein, post operative fatigue, postoperative joint range, post operative pain during rest and weight bearing, and length of hospital stay.

4.2 Hypothesis:

If hypothesis will get confirmed, then the peri operative use of 2 doses of dexamethasone with intravenous tranexamic acid, reduces the postoperative C-reactive protein, post operative fatigue, pain during rest and weight bearing, and length of hospital stay and improves the post operative joint range of motion.

If hypothesis will not get confirmed, then the peri operative use of 2 doses of dexamethasone with intravenous tranexamic acid, will not reduces the postoperative C-reactive protein, post operative fatigue, pain during rest and weight bearing, and length of hospital stay and and will not improve the post operative joint range of motion.

5. Material and Methods:

5.1 Study Design:

Randomized controlled trial with 2 arms

Arm 1: GROUP A will receive 1 dose of dexamethasone (10mg) with tranexamic acid (20mg/kg), peri operatively .

Arm 2: GROUP B will receive 2 doses of dexamethasone (2*10mg) with tranexamic acid (20mg/kg), peri operatively.

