7 STUDY TREATMENT (OR INTERVENTION)

7.1 Regimens (or Intervention), Administration, and Duration

All patients will randomize into two groups,

Group A: 1 dose of IV Dexamethasone 10mg+ tranexamic acid (20 mg/kg);

Group B: 2 doses of IV Dexamethasone 10mg+ tranexamic acid 20 mg/kg.

In group A, 1 dose of 10 mg of intravenous dexamethasone and 20mg/kg of intravenous tranexamic acid administered at 10 minutes before surgery.

In group B, dose of 10 mg of intravenous dexamethasone and 20mg/kg of intravenous tranexamic acid administered at 10 minutes before surgery and then 10mg of intravenous dexamethasone will be again administered before incision closure.

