8.2 Laboratory Evaluations

Pre Operative laboratory evaluations will include:

Complete Blood Count (CBC)

C-Reactive Protein (CRP)

Renal Function Test (RFT)

Hepatitis B and C

Electrocardiogram

Chest X-ray

Activated Partial Thrombin Time (aPTT)

Prothrombin Time (PT)

Hemoglobin A1c (HbA1c)

Post operative laboratory evaluations

Complete Blood Count (CBC)

C-Reactive Protein (CRP)

from which investigators will take data of C-reactive protein values in our study, to compare pre and post operatively.

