8.3 Questionnaires

- Post operative identity consequences fatigue rating scale
- Numeric Pain rating Scale

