10.3 Determination of Sample Size and Power Calculation

The calculated sample size, using total blood loss is 25 in each group and after adding 20% dropout the sample size will be $25+5=30$ in each group. The sample size is calculated using following information.

$Z_{1-\alpha/2}$ Level of significance=95%

μ_1 Expected mean change in total blood loss in Group A=93.80

μ_2 Expected mean change in total blood loss in Group B= 95.98

δ_1 Expected standard deviation in group A=3.88

δ_2 Expected standard deviation in group B=2.82

$Z_{1-\beta}$ power of the study= 80%

sample size in a group(n)= 38

After adding 20% drop out $38+8=46$ in each group.

Total sample size will be 92

No of groups/arms in study:

Type of comparison:

Superiority comparison

Type of configuration:

Parallel designs

Level of significance (Alpha level): 95 %

Power: 0.8 or 80 %

Allocation ratio: 1:1

Underlying population event rate:

Almost 90 percent of population undergoing total joint replacement, whether uni or bilateral would show the positive clinical outcomes with the use of 2 doses of dexamethasone.

Effect size of therapy: the clinical guidelines shows that each group of clinical trial must have at least 30 participants, so effect size is 92 more than sample size calculated, drop out patients percentages added.

Estimated loss to follow-up or refusals: Based on previous work in this population, 20 % will be lost to follow up or drop out from the trial.

10.4 Underlying population event rate:

The population enrolled in previous studies undergoing total joint replacement, whether unilateral or bilateral showed the positive clinical outcomes with the use of dexamethasone with tranexamic acid.

10.5 Estimated loss to follow-up or refusals: Based on previous work in this population, 20 % will be lost to follow up or drop out from the trial.

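### The sample size and 80% power rest on total blood loss, which is not an outcome of the trial, so as written no listed outcome has a supported power

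*Protocol*

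**What the plan says.** Section 10.3 of the protocol names total blood loss three times: in the opening sentence and in the labels of both group means. Group A is given 93.80, and for Group B the entry is "Expected mean change in total blood loss in Group B= 95.98". The SDs are 3.88 and 2.82, and no unit is given. From these the section states 38 per group, 46 after a 20% dropout allowance, and 92 in total, at 80% power.

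The primary objective (4.1) is to evaluate two doses of dexamethasone "on postoperative C-reactive protein, post operative fatigue, postoperative joint range, post operative pain during rest and weight bearing, and length of hospital stay". The hypothesis (4.2) covers the same outcomes. The rationale (section 3) describes the unanswered question as the effect "on post operative range of motion and pain during rest and weight bearing on operated limb, length of stay in hospital and C-reactive protein". Blood loss is in none of these.

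The data-collection text agrees with the objective:
- Section 8.2 orders several laboratory tests, "from which investigators will take data of C-reactive protein values in our study, to compare pre and post operatively".
- Section 8.3 lists a numeric pain scale and the "Post operative identity consequences fatigue rating scale".
- Section 11.2 trains nursing staff to record CRP, range of motion, fatigue, length of stay and pain.

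Outside section 10.3, blood loss appears only in section 2, as background: "TXA can prevent the activation of plasminogen and delay fibrinolysis and reduce blood loss and the rate of blood transfusion perioperatively". Under section 7.1 both arms receive tranexamic acid at 20 mg/kg; the two-dose arm is "Group B: 2 doses of IV Dexamethasone 10mg+ tranexamic acid 20 mg/kg".

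The entry in section 10.3 headed as the effect size of therapy gives a minimum of 30 participants per group and then a headcount: "so effect size is 92 more than sample size calculated, drop out patients percentages added".

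**The concern.** A power statement holds for one variable, one difference and one SD. Here the variable is outside the trial's own objective and hypothesis, and it is the only power statement in the protocol. A reader cannot tell whether 92 patients are too few, enough or more than needed for CRP, fatigue, joint range, pain or length of stay. If the trial ends with a null result on one of these, the stated 80% gives no help in judging whether a worthwhile effect has been ruled out.

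The inputs also look odd for the variable named. They have no unit. Read literally, the arm with the extra dose is expected to have the larger blood loss (95.98 against 93.80). The sign does not change the sample size, but it raises the question of whether the figures describe blood loss at all.

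**Working it through.** **1. Inputs, all from section 10.3.** Means 93.80 and 95.98, so the difference is 2.18. SDs 3.88 and 2.82. Power 80%. Allocation 1:1. The alpha level is written as 95%; I read it as 0.05, two-sided, because the symbol used is Z with subscript 1−α/2.

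**2. Reproducing the plan's figure.**

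n per arm = (z₀.₉₇₅ + z₀.₈₀)² × (SD_A² + SD_B²) / difference²

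= (1.95996 + 0.84162)² × (3.88² + 2.82²) / 2.18²

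= 7.849 × (15.054 + 7.952) / 4.752 = 37.997, so **38 per arm**.

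Adding 20% gives 38 + 8 = 46 per arm and 92 in total, as stated. The 38 and what follows from it are therefore derived from the inputs labelled blood loss. The section also states 25 per group (30 with dropout). That does not follow from these inputs: with 25 per arm the power is about 62%.

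**3. What the 80% refers to.** Average SD = √[(3.88² + 2.82²)/2] = 3.392. Standardised difference = 2.18 / 3.392 = 0.643. The 80% applies to a 0.64 SD difference in the variable labelled total blood loss, and to nothing else.

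**4. What exists for the listed outcomes.** No listed outcome has an expected difference or SD. The effect-size entry is a headcount. The statement that almost 90% of patients will have positive outcomes is not an input to a power calculation for any of them. Their power cannot be computed from the protocol.

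**5. How far the answer could range.** The standardised effects below are my assumptions; the protocol gives none for a listed outcome. The calculation is a two-sample t-test, two-sided alpha 0.05. The 37 evaluable per arm is 46 × 0.8 = 36.8, rounded.

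| Assumed effect (SD) | Power, 46 per arm | Power, 37 per arm | Evaluable n per arm for 80% |
|---|---|---|---|
| 0.3 | 30% | 25% | 176 |
| 0.4 | 48% | 40% | 100 |
| 0.5 | 66% | 56% | 64 |
| 0.6 | 81% | 72% | 45 |
| 0.8 | 97% | 92% | 26 |

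**6. Detectable difference at the planned size.** On the same test, 80% power needs about 0.59 SD with 46 per arm and 0.66 SD with 37.

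**The case against.** The strongest reply is that only the label is wrong. The opening sentence of section 10.3 ties blood loss to 25 per group, while the inputs beneath it yield 38, so the wording may be left over from another calculation. The higher mean in the two-dose arm also fits the one listed outcome expected to rise, joint range. If so, the 80% already covers a listed outcome. This is plausible, but it is inference: both means are labelled blood loss and nothing in the protocol says otherwise. Even if confirmed, the 80% would cover that one outcome and none of the others, and the text would still need amending.

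Second, it is not proven that blood loss goes unrecorded. A blood count is taken before and after surgery, and the four data forms are not reproduced. That stands, so the firm ground is absence from the objective and hypothesis; the data-collection lists are supporting evidence. The tranexamic acid background likewise does not show that blood loss could not be an endpoint. It shows only that the protocol credits reduced blood loss to a drug both arms receive at the same dose.

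Third, the power table uses assumed effects and would look the same for any trial of this size; t-test figures may also carry over poorly to rating scales or length of stay. Both points are fair. The table shows how wide the uncertainty is, not the power of this trial.

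Fourth, the 37 evaluable arises because dropout was added as a multiple of 1.2 and falls just short of the plan's own 38. The effect is small: 0.66 SD against 0.65 SD detectable.

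**Conclusion.** The concern holds as written. The arithmetic behind 38, 46 and 92 is correct, but it is attached to a variable outside the trial's objective and hypothesis, so the 80% supports no outcome the trial sets out to evaluate. The size of the shortfall or surplus cannot be determined from the protocol. Over assumed effects of 0.3 to 0.8 SD, the evaluable number needed per arm runs from 176 down to 26, so 46 could be far too few or more than enough.

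The conclusion depends on taking the label at face value and on reading alpha as 0.05 two-sided; the protocol gives no basis for another label. It does not impugn the between-arm comparisons, which remain valid. It should be corrected because it is the protocol's only power justification.

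**What to change.** First, the sponsor should state what 93.80 and 95.98 measure. Then one of these routes applies:

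- **The figures belong to a listed outcome.** Correct the label in section 10.3, add the unit, time point and source, and name that outcome in section 4.1 as the one that sizes the trial.
- **The figures really are blood loss.** Replace them in section 10.3 with one listed outcome at one time point, named in section 4.1, with its expected difference, SD, unit and source, and recompute the sample size.
- **Enrolment stays at 92 whatever the new calculation gives.** Replace the bare 80% with the difference detectable for the named outcome: about 0.59 SD with 46 per arm and 0.66 SD with 37 evaluable, converted to that outcome's units. This describes what 92 patients can show. It justifies the number only if that difference is also argued to be clinically relevant.

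In every case, replace the headcount in the effect-size entry with the difference used.

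The cost is a text amendment to sections 4.1 and 10.3. Correcting the label or restating the detectable difference needs no extra patients; recomputing for a new outcome may change the number. The stated power may look less favourable afterwards.

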5.3 Duration of study

12 months

8 patients per month will be enrolled

5.4 Trial Population:

Screening Criteria

After giving the informed signed consent, participants will have a detailed examination and will assess for eligibility as defined in inclusion/exclusion criteria.

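### Adding 20% of 38 does not cover a 20% loss: 46 per arm leaves 36.8 completers and 78.7% power on the protocol's own formula, not 80% (a minor error)

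*Protocol*

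**What the plan says.** Section 10.3 sizes the trial on total blood loss. The Group A input reads "Expected mean change in total blood loss in Group A=93.80". Group B has a mean of 95.98, and the standard deviations are 3.88 (A) and 2.82 (B). The power target is "Power: 0.8 or 80" per cent, and the allocation is 1:1. From these the section obtains 38 per arm and continues: "After adding 20% drop out $38+8=46$ in each group". It concludes: "Total sample size will be 92".

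On loss, the section says: "Based on previous work in this population, 20 % will be lost to follow up or drop out from the trial". Section 10.5 repeats this. No other section gives a lower rate or a different reason for choosing 46.

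Section 10.3 also opens with a different result: 25 per arm, raised to 30 for dropout, introduced as coming from the inputs listed beneath it. Section 5.3 gives the recruitment rate over 12 months: "8 patients per month will be enrolled".

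**The concern.** The expected loss is a share of the patients who enter the trial, but the allowance is a share of the patients who must finish it. These are different bases, and the second always gives too small an allowance. The 38 has no slack, since the formula gives 37.997 before rounding, so even a small shortfall in completers takes power below the stated 80%.

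What is at stake is whether the sample size statement is right. Total, loss rate and power are given together, and they do not agree. The statement is likely to be carried into later reports. The extra line giving 25 and 30 per arm adds to the problem, because a reader cannot tell which calculation the trial rests on.

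**Working it through.** **Inputs (all from section 10.3).** Means 93.80 and 95.98, so the difference is 2.18. SDs 3.88 and 2.82. Power 0.80. Allocation 1:1. The significance level is printed as "Level of significance (Alpha level): 95" per cent. I read this as 95% confidence, so alpha = 0.05, and as two-sided because the section writes its Z term with alpha/2. Loss 20%.

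**1. Reproduce the 38.**

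n per arm = (z for 1 − alpha/2 + z for power)² × (SD_A² + SD_B²) / difference²

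- SD_A² + SD_B² = 15.0544 + 7.9524 = 23.0068
- difference² = 2.18² = 4.7524
- n = (1.960 + 0.842)² × 23.0068 / 4.7524 = 37.997 (unrounded z values), rounded up to 38

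The protocol's figure reproduces. A one-sided test would give 30, which supports the two-sided reading.

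**2. Reproduce the 46.** 38 × 1.2 = 45.6, rounded up to 46; 2 × 46 = 92. The allowance is therefore additive.

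**3. Apply the stated loss.** 46 × 0.8 = 36.8 completers per arm (73.6 in total), against 38 (76 in total). The shortfall is 1.2 per arm.

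**4. Power at the expected number of completers.**

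Power = Φ(2.18 / √(23.0068 / n) − 1.960)

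| Loss from 46 per arm | Completers per arm | Power |
|---|---|---|
| 0% | 46 | 86.9% |
| 17.4% | 38 | 80.0% |
| 20% | 36.8 | 78.7% |

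Rounding the completers to whole patients gives 78.9% at 37 and 77.8% at 36.

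**5. Loss that 46 can absorb.** 1 − 38/46 = 0.174, or 17.4%.

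**6. Inflation by division.** 38 / 0.8 = 47.5, so 48 per arm and 96 in total. Expected completers are 48 × 0.8 = 38.4 per arm, which meets the 38. Stated accrual is 8 × 12 = 96.

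**7. The 25 + 5 = 30 line.** With the same inputs, 25 per arm gives power of 62.3%. It cannot be the answer to a calculation that also yields 38. It uses the same additive rule (25 × 1.2 = 30, and 30 × 0.8 = 24), but the contradiction with 38 is the more serious fault.

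**The case against.** The strongest objection is that this hardly matters. The gap is 1.2 completers per arm and 1.3 points of power, and the 20% is itself a round planning figure. That stands, and it is why the point is minor. It does not make the printed combination of 46 per arm, 20% loss and 80% power correct.

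A second objection is that the full 20% may not apply to the variable used for sizing. Sections 7.3 and 9.2 tie non-compliance and discontinuation to the visits at weeks 1 and 4 after discharge, and some of the data are collected in hospital. This softens the point but does not remove it, because section 10.3 applies the 20% to this calculation without qualification and counts all dropout.

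Three stronger readings are tempting, and the documents do not support them.

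- A reader might infer that the trial must enrol 96. The division rule gives 96 on this formula, but a corrected statement of what 92 delivers is equally honest, and the power lost is small.
- A reader might infer that 38 is itself too low because a t-test needs slightly more. The protocol writes its calculation in Z terms, for which 38 is right. Section 10.2 refers only to inferential and descriptive statistics and names no t-test.
- A reader might link this error to follow-up running past the 12 months in section 5.3. At 92 patients, enrolment already takes 92/8 = 11.5 months, so that question exists with or without the correction.

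**Conclusion.** The point holds as a minor arithmetic error. Under the protocol's own 20% loss, 46 per arm leaves 36.8 completers rather than 38. Power by the protocol's own formula is 78.7% rather than 80%, and 80% is kept only if loss is at most 17.4%. Separately, 25 per arm contradicts 38 per arm from the same inputs.

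This rests on reading the printed 95% as a two-sided alpha of 0.05, on the normal approximation, and on the 20% applying to those enrolled. All power figures here are for total blood loss, the variable used in section 10.3. It is not among the outcomes named in the primary objective (section 4.1), so neither 92 nor 96 establishes power for those outcomes. Correcting the dropout step should not be taken as repairing that separate matter.

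**What to change.** In section 10.3, replace the statement on dropout with wording such as:

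> With 38 evaluable patients per arm the power is 80% (normal approximation, two-sided 5%). Enrolling 46 per arm (92 in total) gives about 79% power by the normal approximation if 20% are lost, or 80% if at most 17% are lost.

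Delete the line that gives 25 per arm and 30 after dropout. Both changes are wording only.

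Optionally, the sponsor may inflate by division instead: 38/0.8 = 47.5, so 48 per arm and 96 in total. That costs four more patients and equals the accrual stated in section 5.3.

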11 DATA MANAGEMENT AND MONITORING

11.1 Key personal description

ROLE OF INVESTIGATOR: supervise and guidance of all study protocols

ROLE OF CO-INVESTIGATOR: allocation, screening and reassessments, at follow ups, of patients.

ROLE OF NURSING STAFF: taking data from patients under supervision of co-investigators.

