8 CLINICAL AND LABORATORY EVALUATIONS

8.1. Timing of Evaluations

8.1.1 Screening: Screening will be done during pre operative evaluations, prior to the enrollment in study. In addition to data being collected on subjects who enroll into the study, demographic, clinical, and laboratory data on screening failures will be captured in a screening log and entered into the database.

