10 STATISTICAL CONSIDERATIONS

10.1 Blinding Procedures

The patients, trial participants, anesthesiologists, and data collectors will be blinded to allocation while assessors will know the allocation.

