11.4 Management of Clinical Data

The patient's data will be kept on the red cap software, and assessor will assign the patients into 2 groups such that group A and B, according to the doses of dexamethasone will be given, but data collector and patients will be unaware of the group randomization.

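### Section 11.1 gives allocation, screening and follow-up reassessment to one role with no stated concealment of the next assignment, and blind scoring of joint range is not assured.

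*Protocol*

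**What the plan says.** **Roles.** Protocol section 11.1 lists three duties for one role: "ROLE OF CO-INVESTIGATOR: allocation, screening and reassessments, at follow ups, of patients". For the nurses it says "ROLE OF NURSING STAFF: taking data from patients under supervision of co-investigators". Section 11.2 has nursing staff trained to collect CRP, goniometer knee range, fatigue, length of stay and pain, again supervised by co-investigators.

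**Allocation.** Section 7.1 says "All patients will randomize into two groups" and describes no procedure for doing so. Section 11.4 says the "assessor will assign the patients into 2 groups such that group A and B". REDCap appears in 11.4 and 11.7 for holding data and forms.

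**Eligibility.** Under the screening criteria in section 5.4, after consent, "participants will have a detailed examination and will assess for eligibility as defined in inclusion/exclusion criteria". Section 8.1.1 adds: "Screening will be done during pre operative evaluations, prior to the enrollment in study". It also requires data on screening failures to be logged and entered in the database.

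**Blinding.** Section 10.1 says "The patients, trial participants, anesthesiologists, and data collectors will be blinded to allocation while assessors will know the allocation". Section 11.4 says that "data collector and patients will be unaware of the group randomization".

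**The concern.** Randomisation protects the comparison only if whoever decides on entry cannot know or influence the next arm. A person who both screens and allocates, with no barrier between the tasks, can defer, discourage or exclude a patient according to the arm that is coming. The groups may then differ before any treatment is given, and no analysis reliably repairs that. This is a matter of trial conduct that the protocol itself fixes, so it is not a detail left to a statistical analysis plan.

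The second, lesser concern is measurement. Joint range read with a goniometer depends on the observer and is one of the outcomes in the primary objective (section 4.1). If the reader, or the reader's supervisor, knows the arm, readings may drift towards expectation. Pain and fatigue are rated by patients who are stated to be blind, length of stay is a recorded value and CRP is a laboratory value, so these are less exposed.

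**Working it through.** The point rests on comparing sections. The only arithmetic is a count.

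**1. Who allocates?** Section 11.1 says the co-investigator; section 11.4 says the assessor. The protocol does not say whether they are the same, so both readings need checking.
- *Same role:* the person who allocates also screens and, by 10.1, knows the allocation.
- *Different roles:* 11.1 and 11.4 name two roles for one task, and 11.1 still gives allocation to the role that screens.

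Either reading needs correcting.

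**2. Does screening involve judgement?** Yes. Section 5.4 has eligibility decided after a detailed examination, and 8.1.1 places this before enrolment.

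**3. Is there a barrier between that judgement and the next assignment?** Section 7.1 states only that patients are randomised. The protocol describes no concealed list, independent holder of the list or release step. REDCap is described for data and forms, not for assignment. The order in 8.1.1 implies that eligibility comes before enrolment. But order is not concealment: a screener who holds the sequence already knows what comes next.

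**4. What narrows the risk?** Sections 5.5 to 5.8 answer that there are none for contraindications, excluded medications, allergy, and dependence or serious illness. Section 5.2 takes patients already scheduled for replacement. So the text at hand gives few discretionary grounds for exclusion. The log in 8.1.1 would help to reveal selective exclusion afterwards. Neither prevents steering through the eligibility judgement that 5.4 retains, the consent discussion or the timing of entry.

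**5. How many allocations are affected?** Section 10.3 first mentions 30 per group but ends with 38 + 8 = 46 per group and a stated total of 92: 46 × 2 = 92. All 92 fall to the role that screens under 11.1. This counts exposure; it does not measure bias.

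**6. Is follow-up scoring blind?**

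| Section | What it implies |
|---|---|
| 10.1, 11.4 | Data collectors are blind |
| 10.1 | Assessors know the arm |
| 11.1, 11.2 | Nurses take the data, supervised by co-investigators |
| 11.1 | Co-investigators do the reassessments at follow-up |

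These can be read together: nurses are the blinded data collectors, and a co-investigator is the unblinded assessor who allocates. Three things stay open: whether *reassessments* means scoring outcomes or clinical review, who the *assessors* are, and whether supervision by the allocating role reaches the scoring.

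**The case against.** **On selection.** The best defence is that there is little to select on. Patients are already listed for surgery, the exclusion sections are answered in the negative, screening failures are logged, and screening comes before enrolment. *Co-investigators* is also plural in places, so different people might do the three tasks. All of this is fair and lowers the risk. It does not close the gap: nothing requires the tasks to be separated, the log works after the event, and entry can be steered through consent or timing without using an exclusion criterion.

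**On measurement.** The defence is stronger. Sections 10.1 and 11.4 agree with each other, and one consistent reading has blinded nurses doing all the measuring. The supervision in 11.2 sits beside training and does not say that supervisors score or alter readings. This stands, and it reduces the point to undefined terms and unblinded supervision.

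**Stronger readings that the document does not support.**
- A reader might infer that the sections flatly contradict each other on blind measurement. The consistent reading above shows that they do not.
- A reader might treat the assessor and the co-investigator as certainly the same person. That is an inference from a shared task.
- A reader might see a contradiction between blinded anesthesiologists in 10.1 and the second injection described only for Group B in 7.1. Section 7.1 does not say who gives that injection, so no contradiction is shown.

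**Conclusion.** The allocation point holds with high confidence. As written, the protocol gives allocation and the judgement of eligibility to one role, names a second role for allocation elsewhere, and conceals the next assignment for none of the 92 planned allocations. The result does not depend on whether the assessor is the co-investigator. What is shown is an opening for selection bias. It is not shown that bias will occur, and the document gives no basis for its size or for an effect on the false-positive rate.

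The measurement point holds with lower confidence, as an ambiguity. It rests on reading *data collectors* as the nurses and on *reassessments* possibly including outcome scoring, neither of which the protocol defines. If it matters, it matters mainly for goniometer joint range.

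The protocol should be corrected, and before patients are allocated, because foreknowledge cannot be repaired in the analysis.

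**What to change.** **Allocation (11.1 and 11.4).** Name one allocating role, the same in both sections. Take each arm from a pre-generated, concealed list, for example in REDCap. Release it only after eligibility and consent are recorded, to an existing team member who does not screen, score or supervise scoring.

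**Measurement (10.1, 11.1 and 11.2).** Define *assessors* in 10.1 and *reassessments* in 11.1. State that the blinded nursing staff take the day 1, week 1 and week 4 measurements, and that no one who knows the allocation scores or supervises scoring.

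**Cost.** Some duties move among existing co-investigators and nurses, so allocation and supervision must sit with different people. REDCap needs set-up work, because the protocol now describes it for data and forms only. The rest is wording. Patients undergo no new procedure.
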